Regarding the second component of HAAF, the blunted counterregulatory hormonal response, recent investigations in rodents suggest a central role of an increased γ -aminobutyric acid (GABA) tone in the hypothalamus with recurrent hypoglycemia (16; 17). A fall in the hypothalamic levels of GABA, the main inhibitory neurotransmitter in the brain, appears necessary for activation of glucose counterregulatory responses during hypoglycemia. Recurrently hypoglycemic animals not only have elevated hypothalamic GABA levels, but they also fail to decrease these GABA levels in response to hypoglycemia (16). Furthermore, local application of glucose prevents this fall in a dose-dependent fashion, resulting in a positive correlation of extracellular glucose and GABA concentrations (17) and mechanistically linking increased glucose availability in this region to blunting of the GABA-regulated counterregulatory hormone release. With recently developed technology (14) (Appendix A, Preliminary studies) we can now test if the same sequence of events occurs in the human brain.

These prior data form the basis for our *working hypotheses* in the current application (Figure 1): In the healthy brain, a drop in plasma glucose results in a drop in brain glucose, as well as a reduction in glycogen (18) and GABA (see Preliminary studies). Following recurrent hypoglycemia, a drop in systemic glucose does not cause a similar drop in hypothalamic glucose levels due to upregulated transport capacity (V_{\max}^t), and thus the signal that leads to glycogen mobilization and a fall in hypoglycemic GABA levels is reduced, thereby blunting the hypoglycemia induced sympathoadrenal response. We will investigate these mechanisms both in healthy volunteers who have been preconditioned with recurrent hypoglycemia (a HAAF model), as well as in patients with type 1 diabetes, in order to distinguish the effects of HAAF alone from those of diabetes. With the elucidation of the contributions of glucose (Aim 1a), glycogen (Aim 1b) and GABA (Aim 2) to the pathogenesis of HAAF, new knowledge will be available that will permit the development of better strategies to prevent and treat this condition, such as pharmaceutical interventions to prevent an increase of hypothalamic GABA levels.

B. INNOVATION

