These data demonstrate our ability to reliably measure GABA and glucose concentrations for the proposed studies in Aims 1a and 2 and support our hypothesis regarding an attenuated hypothalamic GABA response to hypoglycemia in type 1 diabetes and hypoglycemia unawareness.

[figure not shown]

Figure 4. Plasma glucose and hypothalamic GABA concentrations in a healthy volunteer (A) and a patient with type 1 diabetes (B) during a hypoglycemic clamp study. Subjects received IV infusions of glucose and insulin. The glucose infusion was stopped at time 0 and restarted later at a lower rate to clamp subjects at 50mg/dl plasma glucose. The healthy volunteer was also studied in a separate session during euglycemia without IV infusions (green circles, A).

C.2. RESEARCH DESIGN

Aim 1a: To measure kinetic parameters for glucose transport and metabolism (K_M transport, V_{max} transport, K_M utilization, V_{max} utilization) in the hypothalamus of subjects with type 1 diabetes with hypoglycemia unawareness and in healthy volunteers preconditioned with euglycemia vs. recurrent hypoglycemia to induce HAAF.

In these experiments, subjects with type 1 diabetes with hypoglycemia unawareness as well as normal controls, preconditioned on separate occasions with euglycemia and with recurrent hypoglycemia, will have hypothalamic glucose concentrations measured continuously using ^1H MRS at 7 tesla over a ~1.5 hour period during which blood glucose concentrations will be experimentally increased from 95 mg/dl to one of 3 target hyperglycemic levels (200 mg/dl (11 mM), 300 mg/dl (16.5 mM), 400 mg/dl (22 mM)).

Study rationale:

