Recent studies in animals suggest that hypothalamic GABA may be important in regulating the counterregulatory response to hypoglycemia and that elevated GABA levels may contribute to the development of HAAF (17). Recurrent hypoglycemia leads to increased basal GABA inhibitory tone in the ventromedial hypothalamus (VMH) and suppresses the counterregulatory response to subsequent episodes of hypoglycemia (16). The role of GABA in regulating the counterregulatory response and in the development of

HAAF in humans is unknown. Therefore, we will use our newly developed ^1H MRS methods to measure hypothalamic GABA in subjects with type 1 diabetes and HAAF and in healthy controls preconditioned with euglycemia vs. recurrent hypoglycemia to induce HAAF. We predict that hypothalamic GABA will be lower during hypoglycemia than euglycemia in controls and subjects with type 1 diabetes, that induction of HAAF will lead to an increase in hypothalamic GABA under both euglycemic and hypoglycemic conditions, and that subjects with type 1 diabetes and HAAF will have higher levels of hypothalamic GABA under both euglycemic and hypoglycemic conditions than euglycemia preconditioned controls (Fig. 7). The MRS acquisition protocol will also provide concentrations of the precursor of GABA, glutamate (Fig. 1), which will potentially provide supporting information about GABA metabolism, however our hypotheses are based on GABA levels, which have been reported to change in prior animal work.

[figure not shown]

Figure 7. Predicted changes in eu- and hypoglycemic GABA levels in hypothalamus (as in Fig. 4) in the healthy brain and in HAAF.

Research Subjects:

Recruitment strategies and inclusion and exclusion criteria will be identical to those in Aim 1a, except we will also exclude subjects who take drugs that can alter GABA metabolism (such as benzodiazepines).

Study Protocol:

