Figure 8. Study protocol for healthy controls in Aim 2.

Euglycemia vs. hypoglycemia states: After preconditioning with euglycemia among the controls, GABA levels will be compared during euglycemia to during hypoglycemia with a repeated measures model with effects for glycemic state, acquisition time (5, 15, etc. minutes, Fig. 4), and their interaction. Correlation structures appropriate for doubly-repeated measures (across acquisition times within glycemic states, for two glycemic states) will be used. These comparisons will be repeated among the controls after preconditioning with hypoglycemia, and among the patients. Pilot work (Fig. 4) shows a standard deviation of the control group difference between euglycemic states and hypoglycemic states of 0.52 $\mu\text{mol/g}$, indicating that with 10 participants we have 85% power to detect paired-group differences of 0.53 $\mu\text{mol/g}$ with type I error of 5%. In the case that standard deviations are twice those observed in Figure 4, we have 85% power to detect differences of 1.10 $\mu\text{mol/g}$. Per-acquisition-time glycemic state comparisons will be adjusted for multiple comparisons using Sidak's method. We have budgeted for 12 participants to allow for two failed scans without sacrificing power. *Patients vs. controls:* Similar comparisons will be carried out between GABA levels in patient euglycemia states and in control euglycemia states after the controls are euglycemic preconditioned. This will be repeated for GABA in hypoglycemic states. Pilot work (Fig. 4) shows a standard deviation of the control group minus patient group difference during the hypoglycemic state of 0.25 $\mu\text{mol/g}$, indicating that with 10 participants we have 85% power to detect paired-group differences of 0.27 $\mu\text{mol/g}$ with type I error of 5%. In the case that standard deviations are twice those observed in Figure 4, we have 85% power to detect differences of 0.53 $\mu\text{mol/g}$. *Preconditioning:* Similar comparisons will be carried out between GABA levels during control euglycemia states for euglycemic preconditioning compared to hypoglycemic preconditioning. This will be repeated for GABA during hypoglycemic states.

Potential pitfalls and solutions:

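### Aim 2 analyses GABA levels state by state but plans no contrast for whether the fall in GABA differs between groups or between preconditionings

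*Combined protocol and SAP*

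**What the plan says.** The data analysis plan for Aim 2 (C.2, Sample size justification and data analysis plan) has three families of comparison.

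1. Euglycemia versus hypoglycemia in controls after euglycemic preconditioning, by a repeated measures model with glycemic state, acquisition time and their interaction. Then: "These comparisons will be repeated among the controls after preconditioning with hypoglycemia, and among the patients".
2. Patients versus euglycemia-preconditioned controls during euglycemia. Then: "This will be repeated for GABA in hypoglycemic states".
3. Euglycemic versus hypoglycemic preconditioning in controls during euglycemia. Then: "This will be repeated for GABA during hypoglycemic states".

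Hypotheses 2a to 2c (Specific Aims) all concern levels: lower in hypoglycemia than in euglycemia, higher in patients than in controls in both states, and higher after hypoglycemic than after euglycemic preconditioning in both states.

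Elsewhere the document addresses the size of the fall. Section A (Significance) reports of recurrently hypoglycemic animals that "they also fail to decrease these GABA levels in response to hypoglycemia", and then says "we can now test if the same sequence of events occurs in the human brain". Its working hypotheses state that, after recurrent hypoglycemia, "the signal that leads to glycogen mobilization and a fall in hypoglycemic GABA levels is reduced, thereby blunting the hypoglycemia induced sympathoadrenal response". Section C.1.4 concludes that the pilot data "support our hypothesis regarding an attenuated hypothalamic GABA response to hypoglycemia in type 1 diabetes and hypoglycemia unawareness". Those data are a 36% fall in one volunteer and a 26% fall in one patient.

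**The concern.** A difference in falls is a difference of differences: the change from euglycemia to hypoglycemia in one set, minus the same change in the other. None of the three families estimates it. The first gives a fall within each set, in separate fits. The second and third give level differences, one state at a time. The only interaction named is glycemic state by acquisition time, within a set.

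The planned results therefore cannot separate two patterns: GABA raised by the same amount in both states with a normal fall, and GABA raised more in hypoglycemia because the fall is smaller. Both satisfy Hypotheses 2a to 2c. Only the second fits the mechanism that Section A links to the blunted sympathoadrenal response. Subtracting the planned level differences would give a point estimate of attenuation, but the plan attaches no interval or test to it. Any statement about attenuation would rest on an informal comparison of separate results.

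**Working it through.** **What each planned analysis estimates.** Write E and H for mean GABA in euglycemia and hypoglycemia, with subscripts p for patients and c for euglycemia-preconditioned controls.

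- Family 1: E_c − H_c and E_p − H_p, fitted separately (and likewise for hypoglycemia-preconditioned controls).
- Family 2: E_p − E_c, then H_p − H_c.
- Family 3: the same two level differences between preconditionings.
- Attenuation: (E_c − H_c) − (E_p − H_p) = (H_p − H_c) − (E_p − E_c). It is in none of the families.

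**Reproducing the plan's figures.** Inputs from the Aim 2 plan: 10 participants, 85% power, type I error 5%. I used a two-sided paired t-test with the noncentral t distribution, for which the detectable difference is 1.066 × SD.

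| SD (µmol/g) | Plan | Recomputed | Power at the plan's figure |
|---|---|---|---|
| 0.25 (level difference) | 0.27 | 0.267 | 85.9% |
| 0.50 (doubled) | 0.53 | 0.533 | 84.6% |
| 0.52 (fall) | 0.53 | 0.554 | 81.8% |
| 1.04 (doubled) | 1.10 | 1.109 | 84.4% |

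Three rows agree. For SD 0.52 the plan's 0.53 is slightly optimistic: 0.55 fits better, and is half the plan's own 1.10. This does not affect the point.

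**SD of the difference in falls.** The plan does not give it. For two paired quantities with common SD s and correlation r, the SD of their difference is s√(2(1 − r)). The correlations below are my assumptions. So is using 0.25, which the plan gives only for patients versus controls in hypoglycemia, for every level difference.

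- From level SD 0.25: r = 0.5 gives 0.250; r = 0 gives 0.354; the limit r = −1 gives 0.500.
- From fall SD 0.52: correlation 0.75 gives 0.368; 0.5 gives 0.520; 0 gives 0.735.

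The two routes constrain each other. With a level SD of 0.25 in both states, the SD of the difference in falls cannot exceed 0.50, so the falls would have to correlate at least 1 − 0.50²/(2 × 0.52²) = 0.54. Uncorrelated falls would need a level SD of at least 0.735/2 = 0.37.

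**Precision with 10 pairs.** The 95% half-width is 2.262 × SD/√10.

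| SD of difference in falls | Detectable at 85% power | 95% CI half-width |
|---|---|---|
| 0.250 | 0.27 | 0.18 |
| 0.354 | 0.38 | 0.25 |
| 0.500 | 0.53 | 0.36 |
| 0.735 | 0.78 | 0.53 |

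If the SDs double, as the plan allows for its own contrasts, these figures double.

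**Pilot gap.** Section C.1.4 gives falls of 36% and 26%, and euglycemic GABA of 3.5–4 µmol/g, but not each person's baseline.

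- Smallest gap: 0.36 × 3.5 − 0.26 × 4 = 1.26 − 1.04 = 0.22.
- Largest gap: 0.36 × 4 − 0.26 × 3.5 = 1.44 − 0.91 = 0.53.
- Equal baselines give 0.35 to 0.40, but Hypothesis 2b expects patients to start higher. With controls at 3.5 and patients at 3.9, the gap is 1.26 − 1.014 = 0.25. Power is then about 80%, 51% and 29% at SD 0.25, 0.354 and 0.50.

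Across the full ranges, power runs from about 14% (gap 0.22, SD 0.735) to over 99% (gap 0.53, SD 0.25). No single power figure is usable.

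**Constructed illustration (level SD 0.25, r = 0, n = 10).** Suppose the level differences in euglycemia and hypoglycemia are 0.40 and 0.40 in one scenario, and 0.40 and 0.75 in another. Each level test has at least 99% power in both, so the planned tests look alike. The missing contrast would have an expected 95% interval of 0 ± 0.25 in the first (−0.25 to 0.25) and 0.35 ± 0.25 in the second (0.10 to 0.60).

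**Why separate tests cannot substitute.** If two sets both truly fall by 0.53 with SD 0.52, each within-set test has 81.8% power. Taken as independent, exactly one is significant with probability 2 × 0.818 × 0.182 = 0.30, although the falls are identical.

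**The case against.** The strongest reply is that no numbered hypothesis goes unanalysed. Hypotheses 2a to 2c are about levels, working hypothesis 2 is about increased GABA tone, and each has a planned comparison. Attenuation appears only in the Significance section and the preliminary studies. That stands. A reader might infer that Aim 2 fails to test its own hypotheses; the documents do not support this. The request is for a secondary contrast, not repair of a broken test.

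A second reply is that families 2 and 3 are described as similar to a repeated measures model, so each may include a group-by-acquisition-time or preconditioning-by-acquisition-time term. If the hypoglycemic acquisitions include the descent in glucose, such a term would bear on whether GABA declines differently. This is a fair reading, but a term within one state does not estimate the euglycemia-to-hypoglycemia difference in falls.

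Third, nothing in the plan says that attenuation will be inferred from separate p-values, and Hypothesis 2a expects a fall in every set. A reader might infer that such a comparison is planned; it is not. The risk is that nothing else is available if the question is taken up.

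Fourth, the Aim 2 rationale has a sentence basing the hypotheses on GABA levels. It distinguishes GABA from glutamate, so it does not settle whether levels or changes are meant.

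Finally, the pilot is one person per group, so neither SD can show variation between pairs. That stands, and is why the results are given as ranges. Figure 7, on predicted changes, is not shown, so whether it predicts a parallel shift or a smaller fall cannot be checked.

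**Conclusion.** The point holds as a gap between the stated mechanism and the analysis plan. Hypotheses 2a to 2c are analysed as written. The further question of a smaller GABA fall, raised in Section A and called a hypothesis in Section C.1.4, has no planned contrast, test or interval. This follows from the text and depends on no figure.

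The size is uncertain. With 10 pairs the detectable difference in falls is about 0.27 to 0.78 µmol/g and the half-width about 0.18 to 0.53, against a pilot gap of about 0.22 to 0.53. These ranges rest on assumed correlations, on pilot SDs from Figure 4 (one volunteer and one patient), and on unstated individual baselines. They would widen if the SDs are larger. A reader might conclude that the added contrast would be well powered, or that it would be hopeless; the documents support neither. The change should be made, but it does not undermine the planned level comparisons.

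**What to change.** Add to the Aim 2 analysis plan one pre-specified secondary contrast, with a 95% confidence interval, for each of two comparisons:

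- patients versus euglycemia-preconditioned controls: the group-by-glycemic-state interaction, clustered on matched pair;
- hypoglycemic versus euglycemic preconditioning in controls: the preconditioning-by-glycemic-state interaction, clustered on subject.

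Each amounts to the paired difference in within-person falls. State the scale in advance as µmol/g, as in the sample size section, since the preliminary data give falls in percent. State the detectable difference as a range with its assumptions. Add that no conclusion about attenuation will be drawn from separate within-set or per-state p-values, and that a null contrast will not be read as absence of attenuation. Leave the tests of Hypotheses 2a to 2c unchanged.

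The cost is a few lines of plan text and two extra contrasts from scans already planned in both states; no new participants or sessions are needed. The downside is that the intervals may be wide, more so if sessions are dropped under the protocol's rule on the epinephrine response.

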The **working hypotheses** for this project are: **1)** recurrent hypoglycemia, like that seen in subjects with type 1 diabetes and iatrogenic hypoglycemia, will lead to an upregulation of glucose availability for the brain (by increased transport, and/or increased glycogen storage), thereby facilitating maintenance of cerebral metabolism during subsequent episodes of hypoglycemia, and **2)** recurrent hypoglycemia will lead to an increased GABA tone in hypothalamus, thereby suppressing glucose counterregulation during subsequent episodes of hypoglycemia. To address these hypotheses we will examine cerebral metabolism in subjects with type 1 diabetes and hypoglycemia unawareness, as well as in healthy volunteers preconditioned with euglycemia vs. recurrent hypoglycemia to induce HAAF, thereby permitting us to understand the clinical syndrome as well as isolate the effects of recurrent hypoglycemia from those induced by diabetes.

Aim 1: To determine the contribution of increased glucose availability in the brain to HAAF

Specific Aim 1a: To measure kinetic parameters for glucose transport and metabolism in the hypothalamus of subjects with type 1 diabetes and hypoglycemia unawareness and in healthy volunteers preconditioned with euglycemia vs. recurrent hypoglycemia to induce HAAF.

Hypothesis 1a.1: Subjects with type 1 diabetes and hypoglycemia unawareness will have a higher V_{\max} transport than will healthy volunteers preconditioned with euglycemia.

Hypothesis 1a.2: Healthy volunteers will have a higher V_{\max} transport following preconditioning with recurrent hypoglycemia than with euglycemia.

Specific Aim 1b: To measure brain glycogen turnover and content by ^{13}C MRS in healthy volunteers preconditioned with euglycemia vs. recurrent hypoglycemia to induce HAAF.

Hypothesis 1b: Subjects will have higher glycogen content following preconditioning with recurrent hypoglycemia than with euglycemia.

Aim 2: To determine the contribution of increased GABA tone in the hypothalamus to HAAF

Specific Aim 2: To measure euglycemic and hypoglycemic GABA levels in the hypothalamus of subjects with type 1 diabetes and HAAF and in healthy volunteers preconditioned with euglycemia vs. recurrent hypoglycemia to induce HAAF.

Hypothesis 2a: Hypothalamic GABA levels will be lower during hypoglycemia than during euglycemia in both normal controls and patients with type 1 diabetes.

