Hypothesis 2b: Hypothalamic GABA levels will be higher both during euglycemia and during hypoglycemia in subjects with type 1 diabetes and HAAF than in matched controls preconditioned with euglycemia.

Hypothesis 2c: Hypothalamic GABA levels will be higher both during euglycemia and during hypoglycemia in healthy volunteers following preconditioning with recurrent hypoglycemia than with euglycemia.

A. SIGNIFICANCE

More than 25 million Americans have diabetes and hypoglycemia is a common event in the lives of patients who receive insulin or insulin secretagogues as therapy for their disease. Inconvenient and disruptive to daily activities, it can also lead to loss of consciousness, seizures, and death. Patients who experience recurrent episodes of hypoglycemia often develop hypoglycemia associated autonomic failure (HAAF); a clinical syndrome in which the first symptom of hypoglycemia is confusion or loss of consciousness (1). The fear of HAAF prevents many patients with diabetes from achieving the glycemic goals known to reduce the risk of developing the microvascular complications of the disease (2). Consequently, better ways to prevent HAAF are of critical importance in advancing care for patients with diabetes. To achieve this goal first requires an understanding of the pathogenesis of this syndrome, which is the purpose of the project outlined in this application.

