Subjects will report to the Center for Magnetic Resonance Research in the morning in the fasting state. *Subjects with diabetes* will be instructed to manage their diabetes in such a way as to minimize the amount of subcutaneous insulin present at the time of study while maintaining adequate control. *Healthy subjects* will serve as their own controls and be studied following the Day 1 hypoglycemia and euglycemia preconditioning protocols described for Aim 1 (Fig. 8). At least six weeks will separate the two studies, which will be done in random order. Female controls will have their two studies two months apart in order to control for phase of menstrual cycle.

On the day of the MRS experiment, an intravenous catheter will be placed antegrade in a forearm for subsequent infusions and a catheter will be placed retrograde in the lower leg for blood sampling. Patients with diabetes will be started on a variable rate infusion of intravenous insulin designed to bring their blood glucose to 95 mg/dl. To adjust the rate, blood will be collected every 5 minutes and tested on a nearby Analox machine. The experiment will begin, for both patients and controls, when the subject is at euglycemia. At time 0, insulin will be started at a rate of 2.0 mU/kg/min, potassium phosphate will be started at a rate of 4 mEq/hr, and glucose (20% dextrose) will be administered at a variable rate to maintain the blood glucose at 95 mg/dl. Subjects will then be placed into the 7 tesla magnet and hypothalamic GABA will be measured. At +60, blood glucose will be reduced to 50 mg/dl. The time course for hypothalamic GABA will be measured as shown in Fig. 4. Samples for the measurement of glucagon, epinephrine, norepinephrine, cortisol, and growth hormone will be collected at minutes 0, 60, 90, and 120. At the completion of the measurement, subjects will be taken out of the magnet, blood glucose will be restored, and subjects will be fed.

^1H MRS methods:

Spectra will be acquired and quantified using identical methods to those described in Aim 1a. We chose to utilize STEAM spectroscopy to quantify GABA levels, as opposed to edited spectroscopy, since the GABA quantification using STEAM was validated against edited spectroscopy (42) and STEAM provides better signal-to-noise and additional metabolite concentrations such as glutamate (the precursor of GABA) and glucose (see Potential pitfalls for Aim 1a).

Sample size justification and data analysis plan:

[figure not shown]

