Prior rodent studies that demonstrated a role for increased hypothalamic GABA tone in blunting the counterregulatory response to hypoglycemia studied the VMH, while our spectroscopic voxel contains a larger portion of the hypothalamus. Despite this pitfall, our preliminary data demonstrate our ability to measure the hypothalamic GABA response to hypoglycemia both in controls and patients with type 1 diabetes. Therefore, we expect to be able to address our hypotheses regarding hypothalamic GABA despite these partial volume effects.

As discussed above, one potential problem we may encounter is that the protocol we use to induce HAAF will not be effective for all subjects enrolled in the study. To ensure that HAAF is present at the time we examine GABA metabolism, we will measure counterregulatory hormones in blood collected from subjects during hypoglycemia. If the epinephrine response (the hormone most blunted during most protocols in which HAAF is induced in humans) during the study done after hypoglycemic preconditioning is $\geq 70\%$ of the response measured during the study after euglycemic preconditioning, we will conclude that HAAF was not induced and the data will not be used for analysis. If HAAF fails to be induced in 1/3, 2/5, 3/7, 4/9,... of the studies (we will monitor in an ongoing way), we will change the protocol to induce HAAF to include more episodes of hypoglycemia before the GABA experiment. In addition, in this aim the blunted counterregulation will also be confirmed in patients with type 1 diabetes by comparing their hormone measurements during the hypoglycemic clamp to those of the euglycemia-preconditioned controls.

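### The only planned H2c analysis in Aim 2 selects controls on epinephrine drawn in the same clamps that supply the GABA values; the likely bias is small, and an all-controls analysis should be reported beside it (minor)

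*Combined protocol and SAP*

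**What the plan says.** **Hypothesis.** Specific Aims, Hypothesis 2c, is worded on the preconditioning received: "Hypothalamic GABA levels will be higher both during euglycemia and during hypoglycemia in healthy volunteers following preconditioning with recurrent hypoglycemia than with euglycemia". The Aim 2 study rationale words the same prediction on the syndrome: "induction of HAAF will lead to an increase in hypothalamic GABA under both euglycemic and hypoglycemic conditions".

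**Sampling.** Under the Aim 2 study protocol, each session is a clamp at 95 mg/dl and then, from +60 minutes, at 50 mg/dl, with hypothalamic GABA measured throughout. Blood for hormones comes from that same clamp: "Samples for the measurement of glucagon, epinephrine, norepinephrine, cortisol, and growth hormone will be collected at minutes 0, 60, 90, and 120".

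**Exclusion.** Aim 2, Potential pitfalls and solutions, compares epinephrine after hypoglycemic preconditioning with epinephrine after euglycemic preconditioning. At 70% or more of the "response measured during the study after euglycemic preconditioning, we will conclude that HAAF was not induced and the data will not be used". If failures are frequent, "we will change the protocol to induce HAAF to include more episodes of hypoglycemia before the GABA experiment". No analysis of all controls is described.

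**Stated link between GABA and epinephrine.** The working hypotheses say that "recurrent hypoglycemia will lead to an increased GABA tone in hypothalamus, thereby suppressing glucose counterregulation during subsequent episodes of hypoglycemia". Section A (Significance) puts it in terms of the change during hypoglycemia: "A fall in the hypothalamic levels of GABA, the main inhibitory neurotransmitter in the brain, appears necessary for activation of glucose counterregulatory responses".

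**Margins.** Aim 1a budgets 15 per group where 12 are needed, and Aim 2 budgets 12 where 10 are needed. Both sample size sections attribute the extra subjects to failed scans alone and say that power is thereby protected.

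**The concern.** The epinephrine ratio is measured alongside the outcome, in the two sessions that H2c compares. On the plan's own reasoning it lies downstream of GABA. Keeping only controls whose epinephrine fell therefore tends to keep controls whose GABA moved in a particular way, even if preconditioning did nothing to GABA on average.

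The direction depends on which of the plan's two statements holds.

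- **Level mechanism** (working hypotheses): higher GABA suppresses epinephrine. Selection then favours H2c.
- **Fall mechanism** (Significance): a larger drop in GABA releases more epinephrine. Retained controls then have smaller drops. The euglycemic-state contrast shifts against H2c and the hypoglycemic-state contrast shifts toward it.

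With the selected subset as the only analysis, a reader cannot separate an effect of preconditioning on GABA from this selection.

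Two smaller points follow from the same rule. It does not say which data are set aside. If the euglycemia-preconditioned session goes too, H2a and H2b lose valid controls for a reason that does not concern that session. And a margin sized for failed scans does not also cover controls lost to non-induction in the within-control comparisons of preconditioning.

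**Working it through.** **1. The plan's own figure.** Aim 2, patients against controls: SD 0.25, difference 0.27 μmol/g, n = 10, paired t-test, two-sided 5%. The noncentrality is (0.27/0.25)√10 = 3.42, and power is 85.9%. The stated 85% reproduces. Exactly 85% needs a difference of 1.066 SD at n = 10, or 0.951 SD at n = 12. The plan gives no separate figure for H2c, so 1.07 SD is an assumption there. For Aim 1a the stated 85% at n = 12 is taken as given.

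**2. Share excluded (h).** Section C.1.1 reports epinephrine at 46 ± 8% of the first response, n = 4, without saying whether ± is an SD or an SE. The gap to the cut-off is 70 − 46 = 24.

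| Reading of ±8 | Normal | t, 3 df, SD × √1.25 |
|---|---|---|
| SD = 8 | P(Z > 24/8) = 0.13% | 3.7% |
| SE = 8, so SD = 8√4 = 16 | P(Z > 24/16) = 6.7% | 13.6% |

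The range is about 0.1–14%. The pilot compared a third with a first clamp, whereas Aim 2 compares two sessions at least six weeks apart, so the Aim 2 share may differ.

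**3. Level mechanism, no true effect.** Let D be a control's GABA difference between sessions, distributed N(0,1). The log epinephrine ratio has correlation −r with D, and controls below the cut c = Φ⁻¹(1 − h) are retained. The documents do not give r; 0.3–0.7 is assumed. The bias is r·φ(c)/(1 − h). For h = 0.14: c = 1.080, φ(c) = 0.2226, 0.2226/0.86 = 0.259, so the bias is 0.08 SD (r = 0.3) to 0.18 SD (r = 0.7).

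Error rates come from 1,000,000 simulated trials of 12 controls with a one-sample t-test on those retained. This is a simplification of the planned repeated-measures model.

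| h | Bias (SD) | Two-sided error, r = 0.3 / 0.5 / 0.7 | Error toward H2c (nominal 2.5%) |
|---|---|---|---|
| 0.13% | up to 0.003 | 5.02 / 5.00 / 4.98% | 2.5% |
| 3.7% | 0.03–0.06 | 5.07 / 5.19 / 5.27% | 3.0–3.6% |
| 7% | 0.04–0.10 | 5.14 / 5.55 / 6.01% | 3.3–4.8% |
| 14% | 0.08–0.18 | 5.60 / 6.68 / 8.30% | 4.1–7.7% |

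Repeat runs differ by up to about 0.1 percentage point, so the top value is quoted as 8.4%. With r = 0.1 or 0, two-sided error is 5.0–5.1% at every share in the table.

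**4. Fall mechanism.** Give the euglycemic-state and hypoglycemic-state differences variance 1 and an assumed correlation of 0.5. Their difference then has variance 1 + 1 − 2(0.5) = 1, and each correlates ±0.5 with it. The bias is ∓0.5·r·φ(c)/(1 − h).

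- At 7%: −0.02 to −0.05 SD (euglycemic) and +0.02 to +0.05 SD (hypoglycemic); two-sided error 5.0–5.2%.
- At 14%: −0.04 to −0.09 SD and +0.04 to +0.09 SD; two-sided error 5.1–5.8%.

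**5. Margins.** The chance of keeping enough controls with no failed scans is P(Bin(15, h) ≤ 3) for Aim 1a and P(Bin(12, h) ≤ 2) for Aim 2. Mean power is noncentral-t power averaged over the binomial number retained.

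| h | Keep 12 of 15 / 10 of 12 | Mean power, no failed scans (1a / H2c) | Mean power, failed scans use whole margin (1a / H2c) |
|---|---|---|---|
| 7% | 98% / 95% | 90% / 89% | 81% / 81% |
| 14% | 85% / 77% | 87% / 86% | 77% / 77% |

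**6. Dilution in an all-controls analysis.** Suppose a 1.07 SD effect exists only in controls with HAAF, and the rule identifies them correctly. Power with all 12 controls is 85% at 7% non-induction and 77% at 14%, against 89% and 86% in the subset.

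**The case against.** The rule is a reasonable check that the manipulation worked. Aim 2 asks what GABA contributes to HAAF, the cut-off is fixed in advance, and frequent failure leads to a stronger induction protocol. A control without HAAF is not informative on that question. This stands, and it is why the HAAF-confirmed analysis should stay. It does not remove the need for the other analysis, because H2c is worded on preconditioning and the check is measured with the outcome.

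The size is also open to challenge. If ±8 is an SD, exclusions are at most about 3.7% and the error rate barely moves. The upper end of r fits poorly with a null effect: if GABA drives epinephrine that strongly, unchanged mean GABA is hard to square with epinephrine falling to 46%. Quantification error (CRLB of 15% in section C.1.4) lowers the correlation with measured GABA. So does partial volume, since "our spectroscopic voxel contains a larger portion of the hypothalamus". This stands too, and it keeps the point minor.

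On the session question, the parallel rules in Aims 1a and 1b compare clamps within one visit, so the natural reading there is that only the hypoglycemia-preconditioned visit is set aside. That reading would leave H2a and H2b intact, but the Aim 2 rule compares two visits and does not say so.

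A reader might infer that Aims 1a and 1b share the selection bias. The documents do not support that: their epinephrine comes from preconditioning clamps before the MRS measurement, and no bias has been shown.

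**Conclusion.** The point holds as a minor one. The only planned H2c analysis conditions on a presumed consequence of GABA measured in the same sessions. Within the pilot's range of exclusion shares, the level mechanism moves two-sided error from 5% to at most about 8.4%, and much less over most of that range. The fall mechanism gives smaller shifts, in opposite directions for the two glycemic states. These sizes rest on two quantities that the documents do not give, the correlation and the share excluded, and on a simplified paired test.

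It would go too far to say that the rule would manufacture a positive H2c result. With a weak correlation or few exclusions, the error rate stays near nominal. Nor do the documents establish that H2a and H2b lose controls; the text is silent on which session is dropped. Nor does non-induction by itself break the 85% power: with no failed scans, mean power stays at or above 85% even at 14%. It falls to about 81% at 7% and 77% at 14% only if failed scans have already used the whole margin.

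**What to change.** - Keep the HAAF-confirmed H2c analysis. Beside it, pre-specify and report, for each glycemic state, an H2c analysis of all controls with both sessions usable. Give 95% confidence intervals for both, and report any disagreement.
- State that the euglycemia-preconditioned session stays in H2a and in the patient–control comparison whether or not HAAF was induced.
- Say that the 85% power for the within-control preconditioning comparison in Aim 1a holds only if failed scans and HAAF exclusions together stay within the margin, and that the Aim 2 margin does not cover HAAF exclusions for H2c.

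This is analysis wording only, with no new subjects, visits or measurements. The drawback is that non-induced controls dilute the all-controls estimate, as step 6 of the working shows. The subset analysis is kept, so its power is not lost.
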